3.1 Assessment and Management of Risk

The table below summarise the risks and mitigations of all test above standard care that are being performed in a table:

Intervention	Potential risk	Risk Management
Assessment with MAPLe device	The device will be placed anally and record sEMG, not providing stimulation. As the device will be used in the same nature as current assessment devices no additional risk is perceived.	Performed by trained operator.

4. Objectives

Primary: To determine the role of MAPLe in the assessment of FI in defined patient groups.

Secondary: To determine if targeted treatment is achieved following assessment with MAPLe.

5. Trial design

This is cohort study of participants with symptoms of faecal incontinence. It will take place across two hospital trusts, both able to provide specialist pelvic floor services and facilities required to meet the needs of the study and follow up required by the participants. The use of two sites aims to increase the yield and diversity of participants. The sample size for the study is 120 participants.

Following a stringent selection and recruitment process, participants will be invited to a designated ARP session where they will be consented, complete an incontinence and quality of life questionnaire, and undergo ARP assessment. This will comprise of the current gold standard, AUS and HRAM, and additional assessment with MAPLe using a standardised protocol. Through undertaking all three tests participants will act at their own controls. Participant participation will conclude following ARP assessment unless treatment is deemed necessary by their local MDT. These participants will be followed up at 6 months with interval MAPLe assessment and incontinence and quality of life questionnaire.

The results will undergo statistical analysis to determine non-inferiority of MAPLe in assessing FI. For analysis participants will be allocated to the following groups: fistula/chronic perianal conditions, obstetric injury <12 months, obstetric injury >12months, neurogenic. Each group will be analysed using symptoms profile and MAPLe results to identify correlation. Comparison of MAPle results pre and post treatment will determine if targeted treatment has been achieved.

An expert panel of pelvic floor specialists will be formed to determine the additional benefit of MAPLe in a clinical context. The panel will consist of 3-6 specialists within the field. To reduce bias,

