each specialist will be provided with literature on the background of MAPLe and how to analyse the results. The panelists will receive up to date guideline on the management of FI. The panel will be provided with cases and ARP results to answer the following questions:

Question 1: What is the additional benefit of MAPLe?

- □ Panelists will be provided with clinical history HRAM and AUS results
 - What is the diagnosis and how will you manage this patient?
- □ MAPLe results provided
 - Has the management changed?
 - How beneficial on scale 1-10 has the addition been?

Question 2: HRAM and AUS vs MAPLe and AUS

- □ Panelists will be provided with a series of paired histories set one with HRAM and AUS results, set two with MAPLe and AUS results
 - What is the diagnosis and treatment?
 - How confident do you feel in your diagnosis and treatment for set two?

Question 3: MAPLe alone

- □ Panelists will be provided with history and MAPLe results
- \Box What is the diagnosis and treatment?
- □ Do you feel enough information is provided by the MAPLe to allow for a management plan?

The outcomes of the expert panel will undergo statistical analysis.

6. Selection of Participants

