11.1 Primary Outcome

They primary outcome is to determine which participant groups benefit from assessment with MAPLe. Benefit will be determined by correct identification of abnormalities in symptomatic participants using MAPLe, correlation between symptom profile and MAPLe results, and the outcome of the expert panel. It will be measured once the end of recruitment is reached.

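### Expert panel: Question 2 gives the same panellists both versions of undefined paired histories, and section 5 has no safeguard against recall between versions or between questions

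*Combined protocol and SAP*

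**What the plan says.** Section 5 (Trial design) sets up a single panel: "The panel will consist of 3-6 specialists within the field". Its task is introduced as "The panel will be provided with cases and ARP results to answer the following questions", and three questions follow.

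- **Question 1, MAPLe as an addition.** "Panelists will be provided with clinical history HRAM and AUS results". After a diagnosis and plan, the MAPLe results are shown. The panellist says whether management changed and answers "How beneficial on scale 1-10 has the addition been".
- **Question 2, MAPLe in place of HRAM.** "Panelists will be provided with a series of paired histories set one with HRAM and AUS results, set two with MAPLe and AUS results". Diagnosis and treatment are asked for, and then "How confident do you feel in your diagnosis and treatment for set two".
- **Question 3, MAPLe on its own.** "Panelists will be provided with history and MAPLe results". Diagnosis and treatment are asked for, and whether MAPLe gives enough information to plan management.

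The measure offered against bias is background reading on MAPLe with instruction in interpreting it. Current guidance on managing FI is also supplied. Section 5 also says that every participant has all three tests and so serves as their own control.

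On use of the result, section 11.1 names three determinants of benefit, and the third, at which this quote breaks off, is the panel's result: "Benefit will be determined by correct identification of abnormalities in symptomatic participants using MAPLe, correlation between symptom profile and MAPLe results, and the outcome of". Section 11.5.1 takes the clinical benefit of adding MAPLe from the panel, and the section 2 summary rests clinical utilisation on it. The panel's analysis is described only as statistical.

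**The concern.** Questions 2 and 3 are meant to show what a specialist would decide with a given set of test results and no others. That requires the reader not to carry over what was learned about the same patient from a different set. Nothing in section 5 secures this: it does not say which cases go to which question, what makes two histories a pair, whether versions are counterbalanced or masked, or how far apart they are read. Reading material on MAPLe teaches panellists to interpret the device; it does not stop them recognising a case.

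At stake is the only part of the primary benefit definition that asks whether MAPLe alters or supports clinical decisions. A Question 2 comparison weakened by recall could make two tests look interchangeable when they are not. A Question 3 answer resting on remembered HRAM and AUS findings could make MAPLe look adequate alone.

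**Working it through.** **No figure of the plan to reproduce.** The documents give no number of panel cases, agreement measure, threshold or model for the panel. The only design figure is the sample size in section 11.3, 4 groups x 30 = 120, which reproduces but was not derived for the panel.

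**Step 1: the possible meanings of the text.**

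| Reading | Supported by | Consequence |
|---|---|---|
| Question 2 pair = one participant, two versions | Own-control statement in section 5; all participants have HRAM, AUS and MAPLe | The history and the AUS result are common to both versions, so the case can be recognised and the plan repeated |
| Question 2 pair = two different patients | Not excluded by the wording | HRAM versus MAPLe is mixed with differences between cases; no matching or assignment rule is given |
| Question 3 reuses cases | Not stated, not excluded | A MAPLe-alone reading can draw on remembered HRAM and AUS results |
| Question 3 uses new cases | Not stated, not excluded | No case recall in Question 3 |

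Neither meaning of a pair gives a protected comparison as the text stands.

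**Step 2: direction in Question 2, by illustration.** Let q be the share of HRAM+AUS plans agreeing with some reference plan, p the share of MAPLe+AUS plans doing so, and c the share of cases in which the panellist repeats the plan made on the version read first. All three are assumptions, and the plan defines no such endpoint. If HRAM+AUS is read first:

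- apparent MAPLe+AUS agreement = p + c(q - p)
- apparent difference = q - [p + c(q - p)] = (q - p)(1 - c)

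| True q, p | c = 0 | c = 0.25 | c = 0.50 | c = 1 |
|---|---|---|---|---|
| 0.80, 0.60 (HRAM better): apparent p | 0.60 | 0.65 | 0.70 | 0.80 |
| apparent q - p | 0.20 | 0.15 | 0.10 | 0 |
| 0.60, 0.80 (MAPLe better): apparent p | 0.80 | 0.75 | 0.70 | 0.60 |
| apparent q - p | -0.20 | -0.15 | -0.10 | 0 |
| 0.70, 0.70 (equal): apparent p | 0.70 | 0.70 | 0.70 | 0.70 |

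Recall shrinks the difference whichever test is better, and has no effect on it when they are equal. If MAPLe+AUS is read first, the HRAM reading becomes q + c(p - q) and the apparent difference is again (q - p)(1 - c).

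**Step 3: Question 3.** For reused cases, let p now be the agreement of MAPLe alone. The same expression p + c(q - p) applies. With p = 0.60 and q = 0.80, half the cases recalled gives 0.60 + 0.50 x 0.20 = 0.70. With new cases c = 0 and the effect vanishes. The expression does not cover the item on whether MAPLe gives enough information, which is a judgement with no reference plan.

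**Step 4: Question 1.** HRAM and AUS first, MAPLe second is the question being asked: what does the addition change? It is not carry-over between conditions.

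**Step 5: are there enough cases to separate the questions?** If recruitment reaches 120 with 30 per group, non-overlapping draws allow up to 120 / 3 = 40 cases per question, or 30 / 3 = 10 per group per question.

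**The case against.** The strongest reply is that this is silence, not a faulty plan. Section 5 numbers the questions and names the sets but states no reading order, never says cases recur, and does not say that a pair is one patient. With fresh cases and different patients there would be no recall at all, and over many pairs case differences might be mere noise. This stands in part. It rules out saying that a fixed order exists or that reuse is planned. It does not rescue Question 2, because different patients with no matching or assignment rule leave the comparison dependent on which cases fell into which set.

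A reader might infer that carry-over always inflates MAPLe. The documents do not support that. In Question 2 recall can hide superiority as well as inferiority, and in Question 1 attachment to the initial plan could lower the rate of changed management. An upward effect is plausible only where HRAM+AUS truly performs better, or where Question 3 cases have been seen before.

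It can also be said that sections 5 and 11.5.1 describe the panel as judging the addition of MAPLe, which is Question 1, so Questions 2 and 3 may weigh little. Section 11.1, however, counts the panel's outcome without restriction, and nothing says how the three questions combine.

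Finally, a strict half-and-half split of readers is impossible with 3 or 5 panellists. That is correct, and the remedy must allow for it.

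**Conclusion.** The point holds conditionally. One panel receives both sets of paired histories and a MAPLe-alone question, with no allocation, counterbalancing, separation in time or masking, and its result enters the primary outcome. On the natural same-participant reading, recall pulls the Question 2 sets together and can hide a true difference either way. On the different-patient reading, the tests are confounded with cases. Question 3 is affected only if cases recur.

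The size cannot be computed. The figures in the working show direction only: with an assumed 20-point true difference, it would appear as 15 points at 25% recall and 10 at 50%. They are not estimates for this trial. Nor do the documents support claims of a fixed reading order, of planned case reuse, or of a defect in Question 1's sequence. This should be settled before the panel meets.

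**What to change.** Amend section 5 and cross-refer from section 11.5.1:

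1. Define a Question 2 pair as the same participant presented in two versions.
2. Draw panel cases at random within each of the four patient groups, with no case used in more than one question. State the number per question.
3. For Question 2, choose one of two schemes. (a) Each panellist reads both versions in separate sessions, with the version read first randomised and counterbalanced per panellist and pair identity masked. (b) Each panellist reads only one version of a case, by a balanced allocation list. With 4 or 6 panellists each version gets 2 or 3 readings per case; with 3 or 5 the split is 2:1 or 3:2, and the larger share alternates between cases.
4. Compare versions within case, with a panellist term. Under (a), add order terms, including version by order, and report first readings separately, since recall of the other version cannot affect them.

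While this text is open, ask for confidence in both versions; it is now requested for set two only and has no comparator.

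The cost is an allocation list and either a second reading session (a) or half the readings per version for the same number of cases (b). For example, 40 cases and 4 panellists give 40 x 4 / 2 = 80 readings per version instead of 160, and the comparison on a given case is then between panellists. No extra participants, panellists or tests are needed.

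### Panel Question 2 asks for confidence with MAPLe and AUS only, so confidence cannot be compared with HRAM and AUS

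*Combined protocol and SAP*

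**What the plan says.** Section 5 (Trial design) describes the panel and its purpose: "An expert panel of pelvic floor specialists will be formed to determine the additional benefit of MAPLe in a clinical context". On size: "The panel will consist of 3-6 specialists within the field".

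The second question is headed "Question 2: HRAM and AUS vs MAPLe and AUS". The material is described as follows: "Panelists will be provided with a series of paired histories set one with HRAM and AUS results, set two with MAPLe and AUS results". Two items follow. The first asks for diagnosis and treatment and names neither set. The second asks "How confident do you feel in your diagnosis and treatment for set two". No response scale is given for it.

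On analysis, section 5 says only: "The outcomes of the expert panel will undergo statistical analysis". Section 11.1 makes the panel outcome one of three determinants of benefit, alongside correct identification of abnormalities and the correlation of symptoms with MAPLe results. The Summary (section 2, statistical methodology row) says the panel's outcome will determine the clinical use of MAPLe.

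**The concern.** Question 2 announces a comparison of two test combinations, but asks for confidence on one side only. It is also the only panel question in which MAPLe takes the place of HRAM while AUS is kept. That makes it the panel question closest to the aim, stated in the Rationale (section 3), of testing MAPLe against the existing tests.

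A confidence rating for MAPLe with AUS has no meaning as a comparison unless the rating for HRAM with AUS is known. High confidence in set two is compatible with equal, lower or higher confidence in set one. If the panel form is used as written, that contrast is lost for good.

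**Working it through.** The check is a count of items in section 5. The plan gives no figure to reproduce.

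**Step 1: list every panel item (paraphrased).**

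| Question | Results shown | What is asked | Confidence rating? |
|---|---|---|---|
| 1 | History, HRAM, AUS | Diagnosis and management | No |
| 1 | MAPLe added | Whether management changed | No |
| 1 | MAPLe added | Benefit of the addition, 1-10 | No (benefit) |
| 2 | Set one and set two | Diagnosis and treatment, neither set named | No |
| 2 | Set two | Confidence in diagnosis and treatment | Yes, set two only |
| 3 | History, MAPLe | Diagnosis and treatment | No |
| 3 | History, MAPLe | Whether MAPLe gives enough information | No (sufficiency) |

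Total: 3 + 2 + 2 = 7 items. Confidence items: set two = 1, set one = 0.

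**Step 2: look for a substitute.** Three items ask for an appraisal. Besides the confidence item, they are "How beneficial on scale 1-10 has the addition been" in Question 1 and "Do you feel enough information is provided by the MAPLe to allow for a management plan" in Question 3. Both appraise MAPLe, and neither measures confidence with HRAM and AUS. At the HRAM and AUS stage of Question 1, only diagnosis and management are asked for. The Summary and sections 11.1 and 11.5.1 mention the panel but add no items.

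**Step 3: what can be estimated.** Let C1 and C2 be mean confidence for set one and set two. The comparison needs D = C2 − C1. C2 is collected and C1 is not, so D cannot be formed for any panel of 3 to 6 members or any number of cases.

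To see how little C2 alone says, assume the confidence item used the 1-10 range of Question 1 (the plan does not say so). For an observed C2 = m, C1 could lie anywhere from 1 to 10, so D lies between m − 10 and m − 1. That range is always (m − 1) − (m − 10) = 9 points wide. It contains zero for every m from 1 to 10.

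**Step 4: can the sets be paired?** Section 5 does not say whether the paired histories are one case shown twice or two matched cases. It does say that every participant has all three tests and serves as their own control. Showing the same case in both sets is therefore feasible and is the natural reading. It needs to be stated, because with different cases a difference in confidence would be mixed with a difference between cases.

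**The case against.** The strongest reply is that Question 2 still delivers a comparison. Its first item is not tied to one set, so diagnosis and treatment can be set side by side. No section names a confidence contrast as an outcome or an analysis, and greater confidence would not show a more correct diagnosis. All of this stands, and it limits the weight of the point. A reader might infer that Question 2 contains no usable comparison at all; the text does not support that.

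A reader might also infer that the analysis of clinical benefit in section 11.5.1 depends on this item. It does not. That section speaks of the benefit of adding MAPLe, which is the design of Question 1, where management before and after MAPLe is recorded. Question 2 concerns substitution. Its links to the plan's conclusions are the general references to the panel outcome in section 11.1 and the Summary, and neither gives a weight to any single item.

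It could be said that the item means confidence relative to set one. The wording does not say so and offers no anchor; if that is the intent, it has to be written down. It could also be said that a fuller panel form exists, but the documents mention none and present these as the questions the panel will answer.

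**Conclusion.** The point holds for confidence only. As written, 0 of 7 items collect confidence with HRAM and AUS and 1 collects it with MAPLe and AUS, on no stated scale. The confidence data cannot show a difference in either direction. This count rests on the text alone and needs no assumption about the number of cases, variability or effect size, none of which the plan gives for the panel.

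The loss is one subjective contrast within one component of the primary outcome. It does not invalidate the panel or the Question 2 comparison of diagnosis and treatment. It should still be corrected, because the correction is cheap beforehand and impossible afterwards.

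**What to change.** Before the panel sits:

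1. Ask the same confidence item, on the same stated scale with labelled ends, for set one and set two.
2. State that the paired histories are the same case shown with each set of results.
3. Randomise or counterbalance, across cases and panelists, which set is seen first, and separate the two presentations of a case. Without this, a set-two minus set-one difference would confound the effect of MAPLe with that of having already seen the case.
4. Specify the analysis. For each case, average the set-two minus set-one difference over panelists. Report the mean over cases with a 95% confidence interval across cases, and show each panelist's own mean difference. With 3 to 6 members, the result describes this panel and not specialists in general.

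The cost is one extra confidence item per case for each panelist, a stated scale and an order list. No additional participants or panelists are needed. The form becomes slightly longer, and some carry-over between the two presentations of a case will remain even with the order controlled.

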11.5 Statistical analysis

11.5.1 Primary outcome analysis

Non-inferiority testing of MAPLe will be performed using Bland-Altman method. Correlation between MAPLe and AUS for location of sphincter abnormality will be identified. Correlation between MAPLe and HRAM for functional abnormalities will be identified.

Participants will be allocated a patient group dependent on the cause of FI:

- □ Fistula/ chronic perianal conditions
- \Box Obstetric injury <12 months
- \Box Obstetric injury > 12 months
- □ Neuropathic

Each group will be analysed using correlation studies and regression analysis to determine which groups benefit from MAPLe assessment.

The clinical benefit of the addition of MAPLe assessment will be determined from the analysis of the results of the expert panel.

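### Panel Question 3 gives history and MAPLe together, with no history-only answer anywhere in the panel, so it cannot show what MAPLe adds to the history

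*Combined protocol and SAP*

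**What the plan says.** Section 5 (Trial design) sets up an expert panel and puts three questions to it. On size, "The panel will consist of 3-6 specialists within the field".

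- **Question 1** is sequential. First, "Panelists will be provided with clinical history HRAM and AUS results" and they give a diagnosis and management. The MAPLe result is then shown and they are asked "Has the management changed", followed by a benefit rating from 1 to 10.
- **Question 2** uses paired histories, "set one with HRAM and AUS results, set two with MAPLe and AUS results", and asks for diagnosis, treatment and confidence in the second set.
- **Question 3** carries the heading "Question 3: MAPLe alone". Under it, "Panelists will be provided with history and MAPLe results". Panellists give a diagnosis and treatment, and are then asked "Do you feel enough information is provided by the MAPLe to allow for a management plan".

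The panel's answers are to be analysed statistically, with no further detail. Section 11.1 makes the panel one of three criteria for benefit in the primary outcome. Section 11.5.1 relies on it for the clinical benefit of adding MAPLe. The Summary says that it determines how MAPLe is used clinically.

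**The concern.** The heading of Question 3 suggests that MAPLe is judged on its own merits, but the panellist also holds the history. On the plan's own account the history may carry much of the answer:

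- **Diagnosis.** In Section 11.5.1, "Participants will be allocated a patient group dependent on the cause of FI". Two of the four groups are an obstetric injury split by its date, and a third is fistula or chronic perianal disease. These are matters that a history will often contain. Section 10.4 lists parity and medical and surgical history among the data collected.
- **Treatment.** Section 3 (Treatment) describes stepwise referral driven by response to treatment and by incontinence scores. Section 5 also gives panellists the management guideline. A plan may follow from these without any probe result.

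If a history-only answer would often have been the same, confident answers to Question 3 are compatible with two opposite conclusions: MAPLe supports management without HRAM or AUS, or MAPLe adds nothing and the history did the work. In a study that sets out to test non-inferiority to HRAM and AUS, these need to be told apart.

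**Working it through.** The plan states no figure for the panel, so there is none to reproduce. The check is whether any combination of panel answers isolates MAPLe's contribution over history.

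**Step 1. Information available at each answer (Section 5).**

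| Answer | History | HRAM | AUS | MAPLe |
|---|---|---|---|---|
| Question 1, first step | yes | yes | yes | no |
| Question 1, second step | yes | yes | yes | yes |
| Question 2, set one | yes | yes | yes | no |
| Question 2, set two | yes | no | yes | yes |
| Question 3 | yes | no | no | yes |

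**Step 2. What the contrasts estimate.**

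- Question 1, second step against first: MAPLe added to history plus HRAM plus AUS.
- Question 2, set two against set one: MAPLe in place of HRAM, given history plus AUS.
- Question 3 against Question 1 (first step) or Question 2 (set one): MAPLe in place of HRAM plus AUS, if the cases are comparable. The plan does not say that they are, or that this comparison will be made.
- MAPLe added to history: this needs a row with history only, and there is none.

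The Question 1 increment could stand in only if MAPLe added as much to history alone as it adds to history, HRAM and AUS together. Nothing in the plan supports that, and tests with overlapping information would break it. Sections 11.1 and 11.5.1 supply no comparator or attribution rule.

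**Step 3. Illustration on assumed values.** The documents give none of these inputs. Suppose answers could be scored as correct. Let h be the share correct from history alone, and m the share of the remaining cases that MAPLe resolves, and assume that MAPLe never spoils a correct answer. Then

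- share correct in Question 3 = h + (1 − h) × m
- MAPLe's gain = (1 − h) × m

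| h | m | Share correct in Question 3 | Gain over history |
|---|---|---|---|
| 0.70 | 0 | 0.70 + 0.30 × 0 = 0.70 | 0 points |
| 0.50 | 0.40 | 0.50 + 0.50 × 0.40 = 0.70 | 20 points |
| 0.30 | 0.20 | 0.30 + 0.70 × 0.20 = 0.44 | 14 points |
| 0.80 | 0.20 | 0.80 + 0.20 × 0.20 = 0.84 | 4 points |

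The first two rows give the same result with different gains: one observed share cannot determine both h and m. In the last two rows MAPLe resolves the same fraction of open cases, yet the higher share correct goes with the smaller gain. If panel answers are broken down by patient group, as the aim in Section 11.1 implies, Question 3 could rank groups by how informative their histories are instead of by what MAPLe adds.

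**The case against.** There is a fair case that this is mostly loose wording.

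- *History is present in every question and only the tests vary, so the heading can mean MAPLe as the only test.* That reading is reasonable, and the line below the heading states openly that history is supplied. Reading a test alongside the history is also how it would be used. Retitling cures the label but does not supply a baseline.
- *Added benefit is the job of Question 1; Question 3 asks about sufficiency.* Question 1 does measure an increment, and for substitution the natural comparator is history plus HRAM plus AUS. But sufficiency of history plus MAPLe says little about the probe if history might have sufficed.
- *The last item of Question 3 asks specifically about information from MAPLe.* This is a partial safeguard. It is a subjective rating made after the history has been seen, so it does not measure what MAPLe changed.
- *Cause group is not the same as the panel's diagnosis.* This stands. Allocation to groups is an analysis step and is not stated to be the panel's task. Section 3 describes the pathogenesis as multifactorial and says that structural and functional assessment is needed to direct treatment. An obstetric history does not by itself separate sphincter damage from pudendal nerve damage, and the neuropathic group may be less evident from history.

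A reader might infer that the plan will credit MAPLe with diagnoses that come from the history, or that most diagnoses are evident from history. The documents support neither: they contain no scoring rule, no reference diagnosis and no figure for what history alone achieves.

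**Conclusion.** The point holds as a limit on what Question 3 can show. History and MAPLe arrive together, no history-only answer exists elsewhere in the panel, and MAPLe's contribution beyond history therefore cannot be estimated. Attribution of history-derived answers to MAPLe is possible; it is not prescribed. The size of any bias cannot be quantified from the documents, and the percentages shown are illustrations on assumed values of h from 0.30 to 0.80 and m from 0 to 0.40.

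A reader might go further and conclude that Question 3 would lead to MAPLe being declared a substitute for HRAM and AUS. The plan has no decision rule by which one panel question could do that, and the panel is only one of three benefit criteria. The missing scoring rule and reference diagnosis for the whole panel are the wider gap. This point is a worthwhile, inexpensive improvement to one of the panel's three questions.

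**What to change.** Split Question 3 into two steps, following the sequential format of Question 1:

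1. History only: record diagnosis and plan, and lock the answer.
2. Add the MAPLe result: record diagnosis and plan again, then ask the existing sufficiency item.

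Analyse the paired change from step 1 to step 2 by panellist and case. Retitle the question *History plus MAPLe (no HRAM or AUS)*.

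Two conditions apply. Step 1 is a true history-only answer only if the panellist has not already seen that case's test results under Question 1 or 2; the plan does not say whether cases are shared, so the panel instructions should. And without a reference diagnosis, the paired change shows whether MAPLe alters the answer, not whether it improves it.

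The cost is one extra answer per case, a few lines of panel instructions and a slightly longer session. No additional participants, visits or tests are needed.
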